#### **9.6.4. Data Entry and Verification of Database Used for Analysis and Reporting**

Data collection is the responsibility of study personnel at the site under the supervision of the site's Investigator. The Investigator is responsible for ensuring the accuracy, completeness, legibility, and timeliness of the data reported.

All source documents should be completed in a neat, legible manner to ensure accurate interpretation of data.

Copies of the study visit worksheets may be provided for use as source document worksheets for recording data for each subject enrolled in the study. Data recorded in the eCRF derived from source documents should be consistent with the data recorded on the source documents.

Clinical data (including AEs, concomitant medications, and expected adverse reactions data) will be entered into an electronic data capture system provided by Lexitas Pharma Services, Inc. The electronic data capture system will be compliant with 21 CFR Part 11. The data system includes password protection and internal quality checks, such as automatic range checks, to identify data that appear inconsistent, incomplete, or inaccurate. Clinical data will be entered directly from the source documents.

#### **9.6.5. Clinical Study Report**

The final clinical study report will be reviewed and approved by the sponsor and, when appropriate, medical, clinical, statistical, and/or regulatory staff from Lexitas.

#### **9.6.6. Inter-Laboratory Standardization Methods**

Not applicable.

### **9.7. STATISTICAL METHODS PLANNED IN THE PROTOCOL AND DETERMINATION OF SAMPLE SIZE**

This section of the analysis plan describes the analyses explicitly mentioned in the protocol as well as additional analyses not explicitly mentioned in the protocol but planned prior to unmasking.. [Section 9.8](#) describes any changes to analyses that were explicitly mentioned in the protocol or statistical analysis plan.

#### **9.7.1. Statistical and Analytical Plans**

##### General Conventions

Summary statistics for the data collected during this study will be presented to give a general description of the subjects studied. Data from all sites will be combined in the computation of these descriptive summaries. Categorical variables will be summarized by the frequency and percentage of subjects in each category. Unless otherwise noted, the denominator to determine

---

the percentage of subjects in each category will be based on the number of subjects with available data. Continuous variables will be summarized using N, mean, standard deviation (SD), median, minimum, and maximum values.

Number of subjects, minimums, and maximums will be calculated to the same number of decimal places as the source data. Means, medians, other quartiles, and confidence limits will be calculated to one more decimal place than the source data. Standard deviations will be calculated to two more decimal places than the source data. Percentages will be calculated to the nearest one decimal place. Zero count cells will be displayed as "0" with percentage of (0%). Unless otherwise noted, summaries will be performed by the treatment group and presented in the order of High Dose, Low Dose, Vehicle.

Results that cannot be calculated (such as standard deviation for a single subject or due to small sample sizes that lead to convergence issues) will be reported as "--".

Statistical tests will be presented as two sided p-values rounded to four decimal places; p values less than 0.0001 will be presented as '<0.0001' and p values=1 will be presented as '>0.9999' in all tables. Unless otherwise indicated, statistical testing will be carried out at the  $\alpha = 0.05$  significance level.

Baseline values will be defined as the last measurement prior to dosing of double-masked study medication. Ocular measurements will use the most recent measurement for each eye.

All data collected in this study will be presented in individual subject data listings for all subjects.

Computations for all results will be performed using SAS Version 9.4 (Version 9.4, SAS/STAT 15.2) computer software package (SAS Institute, Inc., 2013, 2020), unless otherwise specified.

#### Strata and Covariates

For analysis of continuous efficacy endpoints, mixed-effect repeated measures (MMRM) models will model the change from baseline of each endpoint as the dependent variable with the baseline measurement of the corresponding endpoint as a covariate with treatment, visit, and treatment by visit interaction as fixed effects.

#### Subgroups

Subgroup analyses may be conducted based on baseline characteristics on a post hoc basis.

#### Multiplicity

For the primary endpoint, a sequential testing procedure will be employed to control the overall Type I error rate at two-sided 5% with respect to multiple comparisons for the following hypotheses: VVN461, 1.0%, to Vehicle (H1) and VVN461, 0.5%, to Vehicle (H2). The testing procedure will be done in a hierarchical order as H1 and H2. If H1 is not significant, then H2 will not be tested. The secondary and exploratory efficacy endpoints will be analyzed regardless

---

of the significance of the primary endpoint analysis. Both, between group and within group, comparisons with p-values that claim statistical significance should be understood to be “nominal,” as they will not be adjusted for multiplicity.

### Missing Data and Outliers

Missing data for continuous endpoints will be considered missing at random with the analysis using mixed model repeated measures. Otherwise, observed data will be analyzed at each visit.

### Visit Windows

The nominal visits listed in the CRF will be used in the summaries. In general, unscheduled visits will not be summarized in tables unless otherwise noted.

### Missing Dates

Missing dates that occur for prior or concomitant medications or AEs will be queried for a date. If no date is obtained, the following imputation rules will apply:

- For start dates, if the given year (or year-month) is the same as study drug administration, the start date will be imputed as study drug administration date; otherwise, missing month-day (or day) will be imputed as '01-01' (or '01').
- For stop dates, missing months will be imputed as '12' and missing days will be imputed as the last day of the month. If this creates a date after discontinuation/completion, the date of discontinuation/completion will be used.

Imputed dates will only be used to classify events or medications, such as occurring before or after the start of treatment. Imputed dates will only be used in tables. Listings will display the available date data.

### Interim Analysis

Not applicable.

## **9.7.1.1. Analysis Populations**

### **9.7.1.1.1. Populations**

The Full Analysis Set (FAS) consists of all subjects who were randomized. Subjects will be analyzed in the group to which they were randomized. This set will be used for the analysis of all efficacy endpoints as the primary analysis.

The Per Protocol (PP) Analysis Set is a subset of the FAS and will include all subjects in the FAS who completed study-required treatment and who followed the protocol without significant deviations. The determination of significant protocol violations will be made prior to locking the final database and unmasking. Reasons for exclusion will include but are not limited to:

- Subjects with poor study-drug compliance

---

- Non-compliance with the protocol
- Prohibited medication use
- Assessments performed out of order
- Visits out of window

Subjects will be analyzed in the group to which they were treated.

The Safety Analysis Set will include all subjects who took at least one dose of investigational product, as indicated on the dosing record. Subjects will be analyzed in the group according to the treatment received. All safety variables will be analyzed using the Safety Analysis Set and only observed data will be included (i.e., missing data will remain missing for the safety analysis).

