5.5.1 Prohibited Medications and Procedures

Medications that are not explicitly prohibited by the protocol may be used, as needed, throughout the study and recorded as concomitant medications. All medications taken by a subject during the study, whether allowed or prohibited, should be recorded as concomitant medications. [Table 1](#) lists the prohibited medications and procedures for the purposes of the study, as well as the minimum timeframes for discontinuation needed for study eligibility.

CONFIDENTIAL

Table 1 Prohibited Medications and Procedures

Medications and Procedures Not Permitted	Timeframe
Ophthalmic (Study Eye)	
Microinvasive glaucoma surgery, any incisional ocular surgery, or intracameral drug depot to lower IOP	Any history and throughout study
Intraocular surgery	6 months before surgery and throughout study (excluding planned cataract surgery)
Laser surgery, limbal relaxing incision procedure, eyelid surgery Note: Limbal relaxing incisions (laser-assisted and non-laser) are allowed in the study eye at Visit 2 (Day of Surgery)	3 months before surgery and throughout study
Contact lenses	Throughout study and within defined windows before Visit 2 (Day of Surgery) 
 a. Polymethyl methacrylate contact lenses b. Gas permeable rigid lenses c. Extended wear or daily soft lenses 
 a. 6 months before surgery b. 1 month before surgery c. 7 days before surgery
Ophthalmic (Non-study Eye)	
Cataract surgery	14 days before Visit 1 (Screening) or will require cataract surgery <1 day after Visit 2 (Day of Surgery)
General	
Other investigational drug or device	30 days before Visit 1 (Screening) and throughout study
Changes to systemic medication that could have a substantial effect on IOP	30 days before Visit 1 (Screening) and throughout study
Corticosteroids, oral or topical NSAIDs, or Omidria® (i.e., phenylephrine and ketorolac injection) Note: Low-dose acetylsalicylic acid (i.e., baby aspirin or similar) is allowed	1 week before Visit 2 (Day of Surgery) and throughout study

Abbreviations: IOP=intraocular pressure; NSAID=nonsteroidal anti-inflammatory drug

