5.5.2 Rescue Medication

Subjects are eligible to be rescued at any time at the Investigator's discretion and placed on appropriate treatment or therapy. Although the use of rescue medication is allowable at any time, advance consultation with the Medical Monitor is preferred, if possible. If a delay in rescue would place the subject at unnecessary risk, the Investigator should proceed with rescue immediately.

The date of rescue medication administration, as well as the name of the rescue medication and dosage regimen, must be recorded as concomitant medications in the eCRF, with a note indicating that the medication was used for rescue. Subjects who require rescue will be counted as treatment failures and undergo follow-up safety assessments and procedures. Every attempt should be made to have subjects continue in the study for safety evaluations, even if subjects discontinue IP. The need for rescue medication itself will not be considered an AE.

CONFIDENTIAL

6 Study Discontinuation/Subject Withdrawal

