6.1 Discontinuation of Investigational Product

A subject may be discontinued from IP at any time if the subject, the Investigator, or the Sponsor feels that it is not in the subject's best interest to continue. Subjects may have IP withdrawn by the Investigator due to an AE or due to the need for rescue. Subjects who have IP withdrawn due to an AE should be followed for at least 1 week for safety monitoring, or until the AE has resolved.

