9.3 Analysis Populations

The Full Analysis Set (FAS) will consist of all subjects who are randomized. Subjects will be analyzed in the group to which they are randomized. This set will be used for the analysis of all efficacy endpoints as the primary analysis.

The Per Protocol (PP) Analysis Set is a subset of the FAS and will include all subjects in the FAS who complete study-required treatment and who follow the protocol without significant deviations. The determination of significant protocol deviations will be made before database lock and unmasking.

The Safety Analysis Set (SAF) will include all subjects who receive at least one dose of IP, as indicated on the dosing record. Subjects will be analyzed in the group according to the treatment received. All safety variables will be analyzed using the SAF, and only observed data will be included (i.e., missing data will remain missing for the safety analysis).

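### The PP completion rule can remove rescued subjects, whom the SAP scores as failures, yet the rescue-dependent analyses are repeated on PP (minor)

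*SAP*

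**What the plan says.** **Membership.** Protocol 9.3 limits PP to FAS subjects "who complete study-required treatment and who follow the protocol without significant deviations", and SAP 9.7.1.1.1 repeats both conditions: the set "will include all subjects in the FAS who completed study-required treatment and who followed the protocol without significant deviations". The SAP adds a non-exhaustive list of exclusion reasons, one of which is "Prohibited medication use". On timing it says: "The determination of significant protocol violations will be made prior to locking the final database and unmasking".

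**Rescue.** Protocol 6.1: "Subjects may have IP withdrawn by the Investigator due to an AE or due to the need for rescue". Protocol 5.5.1, Table 1, bars corticosteroids for a period given as "1 week before Visit 2 (Day of Surgery) and throughout study"; its only note for that row concerns low-dose acetylsalicylic acid, not rescue. Protocol 5.5.2 reads differently: "Although the use of rescue medication is allowable at any time", consultation with the Medical Monitor is preferred. The same section requires rescue medication to be entered in the eCRF "with a note indicating that the medication was used for rescue".

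**Analyses on PP.** SAP 9.7.1.5.1 identifies rescue as a topical corticosteroid in the study eye and scores a rescued subject as a primary-endpoint failure. It adds an observed-data analysis that drops this failure rule, and repeats both on PP. The proportion of subjects needing rescue before Day 14 is a secondary endpoint (SAP 9.7.1.5.2). Secondary endpoints are also analysed on PP (Protocol 9.4.2; SAP 9.7.1.1.2 and 9.7.1.5).

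**The concern.** PP is the designated sensitivity set for the primary and secondary endpoints. One of its membership conditions can be failed as a direct result of rescue, and rescue is an outcome: it makes a subject a failure on the primary endpoint and is a secondary endpoint in its own right. A set that sheds such subjects is selected on outcome. How many it sheds is left open. The completion condition catches those whose drug is stopped, and the prohibited-medication reason may or may not catch the rest.

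At stake is how the PP results can be read. If PP and FAS differ, part of the gap may come only from the removal of scored failures. If they agree, opposite effects in the two arms may have cancelled. The PP rescue proportion would describe a set from which some or all rescued subjects had been taken out.

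**Working it through.** **Step 1. Two routes out of PP.**

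- *Completion.* A subject whose drug is withdrawn for rescue (Protocol 6.1) has not completed the required treatment (Protocol 9.3; SAP 9.7.1.1.1). This follows from the plain wording. Withdrawal is optional, so the route covers an unknown share of rescued subjects.
- *Prohibited medication.* Rescue is a topical corticosteroid (SAP 9.7.1.5.1), Table 1 bars corticosteroids during the study, and neither Table 1 nor the SAP's exclusion list excepts rescue. This is one of two readings. Protocol 10.1.8 defines a deviation as non-compliance, Protocol 5.5.2 permits rescue, and masked review decides which deviations are significant.

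**Step 2. The planning figures used as a base** (Protocol 9.2; SAP 9.7.2). With 30 per group, 30% on Vehicle, 65% on active (30% + 35 points) and a two-sided 0.05 Pearson chi-square test, power is 79.0% by the normal approximation and 79.8% by exact enumeration; the plan states 80%. For drop-out, 30/(1 − 0.10) = 33.3, rounded up to 34 per group, and 3 × 34 = 102, as stated. These figures supply only the two response rates used below.

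**Step 3. Effect of removal on the primary difference.** Let p be an arm's composite response rate in the FAS, r its rescue rate and f the share of rescued subjects removed. Every rescued subject is a composite failure, so removal shrinks the denominator only:

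PP rate = p / (1 − f·r)

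The documents give no rescue rates, so all values of r and f are assumptions. No other PP exclusions and no missing data are assumed.

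| Rescue, Vehicle/active | PP difference, all removed (f = 1) | PP difference, half removed (f = 0.5) |
|---|---|---|
| 40%/10% | 0.65/0.90 − 0.30/0.60 = 0.722 − 0.500 = 22.2 points | 0.65/0.95 − 0.30/0.80 = 30.9 points |
| 20%/10% | 0.65/0.90 − 0.30/0.80 = 0.722 − 0.375 = 34.7 points | 0.65/0.95 − 0.30/0.90 = 35.1 points |
| 20%/20% | 0.65/0.80 − 0.30/0.80 = 0.8125 − 0.375 = 43.8 points | 0.65/0.90 − 0.30/0.90 = 38.9 points |

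The FAS difference is 35 points throughout. With f = 1 the shift is 0.65·rA/(1 − rA) − 0.30·rV/(1 − rV), where rA and rV are the active and Vehicle rescue rates. It is zero when the Vehicle odds of rescue are 0.65/0.30 = 2.17 times the active odds. Above that ratio PP understates the FAS difference; below it, PP overstates.

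**Step 4. Effect on the PP rescue proportion**, which is r(1 − f)/(1 − f·r). With f = 1 it is 0% in every arm. With f = 0.5, true rates of 40%/10% appear as 0.20/0.80 = 25.0% and 0.05/0.95 = 5.3%; true rates of 20%/20% appear as 0.10/0.90 = 11.1% in both arms.

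**Step 5. The with/without-rescue pair.** With f = 1 the rescue-failure rule has nobody in PP to act on, so switching it off changes nothing.

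**The case against.** The best defence is that nothing here is contradictory. Rescue is expressly permitted, so using it is not obviously a deviation. Only significant deviations exclude, and these are judged while treatment is masked. The PP repeats are blanket instructions, and repeating an analysis on a subset does not promise that every event type occurs in it. At worst one table is uninformative and two coincide, and only if every rescued subject is removed. PP is supportive, and the planned PP counts by arm (SAP 9.7.1.2) and list of excluded subjects (Protocol 9.4.1) would show uneven removal.

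Much of this stands, and it rules out three stronger readings that a reader might infer:

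- *That the SAP excludes all rescued subjects.* It does not say so. The prohibited-medication route depends on interpretation, and the completion route applies only where drug is stopped.
- *That the PP analyses presuppose rescued subjects, so the plan contradicts itself.* The analyses lose information without them, but they can still be run.
- *That PP-versus-FAS agreement can never indicate robustness.* At 20%/10% the two differences are nearly equal (34.7 against 35), and the size of any shift depends on rates the documents do not give.

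The defence does not answer the completion route. Completion is a separate condition from the absence of significant deviations, so review of deviations does not by itself keep a subject who stopped drug. Masking prevents selection by treatment, not by outcome. Counts and lists show a removal only after it has been made.

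A sponsor could instead choose a PP set of completers only and drop or explain the PP rescue analyses. That is coherent and closer to Protocol 9.3, but it too has to be written down.

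**Conclusion.** The point holds as a minor one that is cheap to settle. A stated membership rule removes some rescued subjects because of an event that the primary analysis scores as failure, and the plan does not say how the others are to be treated. To the extent they are removed, the PP rescue proportion moves toward 0% and the PP primary difference can move either way. With full removal it is 22 to 44 points against 35 in the scenarios shown, all of which rest on assumed rescue rates and the planning response rates.

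The FAS primary analysis, and the observed-data and multiple-imputation analyses on the FAS, are untouched. Secondary p-values are nominal (SAP 9.7.1, Multiplicity), and no decision rule uses PP.

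The completion wording also removes subjects who stop treatment early for lack of efficacy or an adverse event; SAP 9.7.1.5.1 scores discontinuation for these reasons before the visit as failure. A reader might take the 10% drop-out allowance as a ceiling on how many there could be. The documents do not support that: the allowance inflates from completed subjects, is not split by reason, and does not address stopping drug while staying in the study. No size is given for this group.

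**What to change.** Before database lock, add to SAP 9.7.1.1.1:

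> Receipt of rescue medication, or stopping IP because of rescue, is not by itself a reason for exclusion from the PP set. Medication recorded in the eCRF as rescue does not count under the exclusion reason "Prohibited medication use" for PP membership.

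Put no scoring rule in the population definition. A clause there making rescued PP subjects failures would conflict with the planned PP analysis that drops the rescue-failure rule. Scoring belongs in 9.7.1.5.1, so that both versions remain possible on PP.

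In the same edit, say whether subjects who stop early for lack of efficacy or an adverse event stay in PP. Record the departure from Protocol 9.3 in SAP 9.8.2.

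The cost is two or three sentences and one log entry. No new data are needed, because rescue is already flagged in the eCRF. The downside is that PP becomes less strictly a set of treatment completers. The change concerns analysis-set membership only and leaves the rules on giving rescue or stopping drug as they are.

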#### **9.7.1.1.2. Analysis Eyes**

The study eye is the eye that meets all inclusion and no exclusion criteria. If both eyes are eligible, the Investigator will designate the study eye. The study eye is the surgical eye. Efficacy analyses will be performed on the study eye using the FAS. Sensitivity analyses will be performed for primary and secondary endpoints using the PP Analysis Set.

Safety analyses will be presented for the study eye and the non-study eye.

#### **9.7.1.2. Analysis of Subject Disposition**

The number of subjects randomized at each site will be summarized by treatment group and overall.

Subjects' enrollment and disposition during the study will be summarized by treatment group and overall. The reasons for discontinuation will be listed in the order as they appear on the eCRF.

Summary tables will include the following. The percentages will be calculated based on the number of randomized subjects.

- Number of subjects screened
- Number and percentage of subjects treated
- Number and percentage of subjects in the Full Analysis Set
- Number and percentage of subjects in the Per-Protocol Analysis Set
- Number and percentage of subjects in the Safety Analysis Set
- Number and percentage of subjects treated who completed the study
- Number and percentage of subjects treated who discontinued from the study
- The reasons for study discontinuation
- Number and percentage of subjects attending each visit

A table of protocol deviations will be presented using the FAS.

---

A listing of subjects who do not meet all inclusion criteria or meet exclusion criteria will be provided.

### **9.7.1.3. Analysis of Demographic and Baseline Characteristics**

#### **9.7.1.3.1. Demographics and Disease Characteristics**

Demographic characteristics include age (years), age group (<65 years, ≥65 years), sex, race, and ethnicity. These characteristics, as well as clinically significant findings during abbreviated physical exam, systolic and diastolic blood pressure, and heart rate, will be summarized descriptively by treatment group and overall using the FAS, PP, and Safety Analysis Sets. For categorical parameters, the percentages will be calculated overall and based on the number of subjects in each treatment group based on non-missing observations.

